Each of the three usual rehabilitation groups will perform usual physical therapy including a home VOR retraining exercise program without the use of the virtual reality headset. The VOR exercise (commonly referred to as the "X1" exercise) will involve holding a piece of paper at arm's length at eye level with an "X" written on the paper. The patient will then rotate their head right and left, reaching 30-45 degrees of excursion in each direction, while attempting to keep their eyes focused on the letter "X". They will then repeat this procedure in the up and down direction. The complexity of the background and duration of exercise will be increased via instruction from the therapist. They will be asked to keep a log of their exercises to assess patient reported compliance. In general, Subjects will be instructed to begin performing the exercises for a duration of 30 seconds at the fastest rate possible so that the 'X' remains in focus and their symptoms are tolerable. As the days progress, Subjects should increase the duration and speed of the exercises as they are able, until they can perform each set for 2 minutes at approximately 1 Hz (1 head shake per second) without any aggravation of symptoms. Once the patient has reached this point, the complexity of exercise background will be increased. Once the background complexity is increased, the patient will be instructed to again start at 30 second exercise bout durations and gradually increase until they are able to achieve 120 seconds without increase in symptoms. Once the patient achieves 120 seconds without symptoms, they will repeat the combination of exercise duration and background complexity increase in the standing position. To perform in a standing position, the patient will be instructed to stand in the corner of a room with a stable chair in front of them to provide a safe environment in which to perform the exercise and by preventing limit chance of falling.

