Subjects in the three intervention groups will be asked to perform the same type of exercises as the usual rehabilitation group, but using a virtual reality device that will be issued to the patient for home use. Subjects will use a custom designed program to perform the exercises using a commercially available virtual reality device (no specialized hardware or additions to the commercially available device will be performed). Subjects will be instructed on the first day in how to operate the Virtual Reality Vestibular Rehabilitation (VRVR) program and how to properly perform the exercises. The VRVR device and software will simulate a virtual reality 'room' with an 'X' fixed in front of a wall. Six different background complexities will be offered: 1) plain grey wall, 2) checker board wall, 3) tight houndstooth wall, 4) visual flow from top to bottom, 5) visual flow to the direction of hypofunction, and 6) visual flow moving away from the nose bilaterally. Exercise sessions will start seated upright in a chair and will progress to standing per the home exercise protocol. The system will prompt the patient to begin the exercise and will automatically log the frequency and duration of exercise performed. The system will ask the patient to rate the severity of their symptoms on a 0-10 scale before and after each bout of exercise. Subjects' instruction regarding initial dose and progression will be identical to those given in the usual rehabilitation group. In addition to the general satisfaction survey given to the usual rehabilitation group, Subjects in the intervention group will also be asked to complete a survey regarding comfort, usability, and satisfaction with the VR instrument and with the VRVR software. Subjects will be asked to bring their device with them to their 4 week, 8 week, and 12 weeks appointment to transfer their de-identified data and to insure integrity of the data and device. Subjects will be asked to return the device at the end of the intervention period.

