Per patient and therapist discretion, additional physical therapy visits may be scheduled to aid in patient understanding of exercise progression protocol, assess correct performance of exercise (with or without virtual reality device). Non-study related physical therapy visits may be scheduled between sessions in order to address impairments unrelated to vestibulo-ocular deficits. These may include interventions to address musculoskeletal deficits or other balance related impairments. Any additional sessions of physical therapy will be reported in order to determine possible confounding information.

There will be an additional group of healthy control subjects that will be tested for only one day. Healthy subjects will be recruited through flyers, approved email lists, and word of

mouth in the general public. This healthy control group will perform the same tests as the other groups perform on Day 1. This group will be used to compare outcomes of usual rehabilitation and intervention groups, to the function of those without disorders of vestibular function.

Statistical Analysis Plan:

Similarities in subject group characteristics will be determined using a one-way ANOVA. Characteristics will include: Age, height, weight, questionnaire scores, and functional outcome scores. A two-way Repeated-Measures ANOVA will be used for analysis of functional outcomes measures for each assessment time (0,4,8, and 12 weeks) for each group of Unilateral Vestibular Hypofunction, Bilateral Hypofunction Dysfunction, and Post Concussion Syndrome compared to their respective controls. A one-way ANOVA will be used to compare functional outcome measures of all groups on the final day of treatment only to healthy control performance. A multiple regression analysis will be used to determine the relationship between the exercise parameters and changes in outcome measures.

Group	Subgroup	Home Program Intervention	Visits	Test performed by all groups
Unilateral Vestibular Hypofunction	Usual rehabilitation	Usual Physical Therapy with patient self-reported compliance log	1) Initial Evaluation 2) 4-Weeks post	Questionnaires  Dizziness Handicap Inventory Activities-Specific Balance Confidence Scale  Visual Vertigo Analog Scale  Visual Analog Score of symptoms
	Intervention	Home exercises using Virtual Reality Vestibular Rehabilitation	1) Initial Evaluation 2) 4-Weeks post	  Functional Assessment

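### The dose regression names no exercise parameters or covariates, and parameters that advance as symptoms allow can show a dose association when exercise has no effect

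*Combined protocol and SAP*

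**What the plan says.** The title asks what dose of vestibular rehabilitation is required for improvement. Under Statistical Analysis Plan, the only regression of outcome on dose reads: "A multiple regression analysis will be used to determine the relationship between the exercise parameters and changes in outcome measures". The section does not say which parameters or outcomes are meant, or over what interval change is taken. It does not say whether baseline score, arm or diagnosis enters, or whether the 4-week cohort (UVH) is pooled with the 12-week cohorts (BVH, post-concussion).

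The Description sets how the parameters move:

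- Duration and speed: "Subjects should increase the duration and speed of the exercises as they are able". For duration and background, the therapist also has a part: "The complexity of the background and duration of exercise will be increased via instruction from the therapist".
- Background complexity: it follows a 2-minute set performed "without any aggravation of symptoms. Once the patient has reached this point, the complexity of exercise background will be increased".
- Reset: at each new background the patient is told to "again start at 30 second exercise bout durations and gradually increase until they are able to achieve 120 seconds without increase in symptoms".
- Posture: "Once the patient achieves 120 seconds without symptoms, they will repeat the combination of exercise duration and background complexity increase in the standing position".

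The VR arms receive the same instructions on starting dose and progression. The VR device "will automatically log the frequency and duration of exercise performed" and asks for a 0-10 symptom rating before and after each bout. Of the usual rehabilitation arms the Description says: "They will be asked to keep a log of their exercises to assess patient reported compliance". The fields of that log are not listed. No text says that speed, background level or posture is recorded. Additional physical therapy sessions are to be reported because they may confound, but they are not made a covariate.

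**The concern.** Randomisation within each diagnosis is to VR or usual rehabilitation, not to a dose, and both arms follow the same progression instructions. Dose therefore varies through behaviour and recovery. A patient who gets better for any reason is allowed longer, faster and more complex exercise, and then exercise while standing. Using those quantities to predict improvement over the same period puts a consequence of recovery among the predictors.

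The problem is sharpest where the outcome resembles the progression rule. The VAS of symptoms is a symptom rating. The VRVR assessment in the table of groups and tests raises background complexity until symptoms rise by 3 points. Under this title, a slope showing only that recovering patients do more could be read as evidence on how much exercise is needed. With predictors and covariates left open, the choice could also be made after the data are seen.

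**Working it through.** The documents give no sample size, alpha, SD or effect size, so there is no stated figure to reproduce. Every input below is assumed unless marked as the plan's. The true dose effect is zero and the test is two-sided 5%, so the correct rejection rate is 5%.

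**Step 1. How much reverse correlation is enough.** Suppose recovery alone induces correlation r between a parameter and the change score. Then

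P(reject) = Φ(√(n−3)·atanh r − 1.96) + Φ(−√(n−3)·atanh r − 1.96).

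For r = 0.3 and n = 60: √57 = 7.550, atanh 0.3 = 0.3095, product 2.337, and P = Φ(0.377) + Φ(−4.297) = 65%.

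| r | n=20 | n=60 | n=100 |
|---|---|---|---|
| 0 | 5% | 5% | 5% |
| 0.2 | 13% | 33% | 52% |
| 0.3 | 25% | 65% | 86% |
| 0.5 | 62% | 99% | 100% |

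**Step 2. What the progression rule can produce.** From the plan: start at 30 s, maximum 120 s, reset to 30 s at each new background, 28 or 84 days. Assumed:

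- Baseline severity b ~ N(0, 1) and recovery g ~ N(1, 0.5), with g unaffected by exercise.
- Tolerance on day d of D at level L is T = −c(b − g·d/D) − 0.25L. Duration rises 15 s with probability 1/(1+e^−T).
- Observed improvement = g + error (SD 0.5).
- Bouts per day are independent of recovery.

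Here c is how strongly tolerance follows symptoms. Rejection rates with n = 60 and 600 trials per row:

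| Days | c | Level reached | Mean bout duration | Mean duration, baseline-adjusted | Total seconds | Number of bouts |
|---|---|---|---|---|---|---|
| 28 | 0 | 5.2% | 5.8% | 5.3% | 5.2% | 4.7% |
| 28 | 1 | 21.0% | 8.2% | 10.7% | 4.7% | 4.3% |
| 28 | 2 | 24.0% | 12.0% | 21.0% | 6.7% | 5.2% |
| 84 | 0 | 4.8% | 5.7% | 6.5% | 4.8% | 4.2% |
| 84 | 1 | 29.5% | 11.0% | 20.7% | 5.2% | 3.8% |
| 84 | 2 | 31.0% | 15.0% | 47.0% | 5.7% | 6.5% |

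Simulation error at 5% is √(0.05·0.95/600) = 0.9 points, so 3.3-6.7% is compatible with nominal. Number of bouts stayed at 3.7-6.5% in every setting run. Level reached is worse than mean duration like for like (both unadjusted; level was not run with baseline). Baseline adjustment raises the error for duration, because it removes variation in tolerance that is unrelated to g. It is not a cure by itself.

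**Step 3. A different recovery model.** Provoked symptoms and outcome each decay exponentially, with n = 30, median half-life 28 days and correlation 0.9 between outcome and provoked symptoms. There were 36 settings per window and 2,000 trials each. For mean bout duration with baseline, 4-week false positives ran 4-74% (median setting 18%). At 12 weeks, rejections of either sign ran 5-79% (median 12%). Session count stayed at 4-6%. At log-SD of recovery rate 0.5, the error for duration fades as the correlation falls:

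| Correlation | 4 weeks | 12 weeks |
|---|---|---|
| 0.9 | 8-50% | 8-58% |
| 0.5 | 4-17% | 7-20% |
| 0.3 | 4-9% | 6-12% |
| 0 | 4-6% | 5-9% |

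A third simulation (n = 30) put level reached at up to 77%, mean duration at up to about 40% (mostly negative at 12 weeks, because of the reset), total time at about 5-9% and sessions near 5%.

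**Step 4. Sign.** In Step 2 the average correlation of mean duration with improvement was positive (0.07 to 0.13 with resets and c of 1 or 2). Under exponential decay without baseline it was often negative, but that depends on sicker patients improving more. When improvement was made independent of starting score (250 trials per setting), the 4-week negative rate fell from 0-60% (median 8%) to 0-3% (median 1%). At 12 weeks it fell from 0-87% (median 10%) to 0-41% (median 2%).

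**Step 5. Pooling and arm.** At equal daily exercise, cumulative dose differs 84/28 = 3-fold by cohort alone. If self-report overstates sessions by 20-30% and arms differ by 0.5-0.8 points, a null sessions slope is significant in 8-16% of trials without an arm term and about 5% with one.

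**The case against.** Five points on the other side have weight.

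- The SAP claims only a relationship. True, but a title about required dose invites the causal reading, and nothing in the SAP guards against it.
- Logged duration may mean total exercise time and not bout length. This stands: the text fits either. Total time is much less affected: near nominal in Step 2, and 7-8% in the median setting of a rebuilt version of the Step 3 model, although its range there was 2-43%.
- The large figures need a correlation near 0.9. This stands. Many listed measures are gait, balance, confidence or ocular tests, and the documents do not say how closely those follow provoked symptoms.
- A multiple regression would enter several parameters together. With sessions and mean duration both in the model, the sessions slope stayed at 2-12% (median 5-6%), but the duration bias did not change. This limits the scope and does not remove the problem.
- The repeated-measures ANOVA at 0, 4, 8 and 12 weeks bears on programme length, which is one side of dose. That is fair. The regression is the only analysis of exercise performed, not the only one touching dose.

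It also counts that background level, the most affected parameter, is not stated to be recorded.

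**Conclusion.** The point holds in a limited form and should be fixed before the regression is run. The parameters and covariates are undefined. Several candidate parameters are partly results of recovery under the plan's own progression rules. For outcomes close to provoked symptoms, the regression can therefore show a dose association that exercise did not cause. The error runs from about the nominal 5% to well above 50% across assumed inputs. It is strongest for level reached, smaller for mean bout duration, and small for total time or session count if attendance does not follow symptoms. Those ranges show what is possible, not what is likely here.

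A reader might infer three stronger things that the documents do not support:

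- That the planned regression will give a false dose effect. Too much is open for that: parameter, outcome, covariates and sample size.
- That leaving out baseline makes the duration slope negative, so that longer bouts would look harmful. This depends on a recovery shape that the documents do not give. With the 30-second reset, the sign is simply unreliable.
- That the trial's main comparisons are compromised. VR versus usual rehabilitation is randomised and is not affected.

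**What to change.** Change SAP wording only; the exercise rules stay as they are.

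1. Make number of sessions completed the single main dose predictor. It is available from the device log, and the compliance log should supply it in the same form. Fit the model within each diagnosis, without pooling the 4-week and 12-week cohorts. Adjust for the outcome score at the start of the window, for arm (device-logged versus self-reported) and for the additional therapy sessions already recorded.
2. Report total exercise time as a secondary exposure. Report bout duration, and speed, background level and posture where recorded, as markers of progression and not as dose.
3. State that the results are observational associations and do not establish the dose that the title calls required.

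A lagged model (weeks 0-4 sessions with week 4-8 change, and weeks 4-8 with 8-12) is optional for BVH and post-concussion. UVH has only weeks 0 and 4, so it allows none. The lagged model can be weak: with n = 30 and an effect only within the window, power was 34% against 76% for the same-window model when adherence correlated 0.5 across windows, and 70% against 78% at 0.9.

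The cost is text, modest analysis work and a compliance log that counts sessions. There are two downsides. Session count does not capture intensity. Confounding also remains if attendance follows symptoms: in the Step 3 model with baseline, rejection rose to 4-11% when attendance shifted 3 percentage points per symptom point, and to 5-25% when it shifted 6.

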**Title: Dose of Vestibular Rehabilitation Required for Clinical Improvements in Individuals With Vestibular Hypofunction**

**NCT04851184**

**Date Approved: 11/13/23**

**Protocol and Statistical Analysis Plan.**

**Description:**

When a potential subject is identified, the subject will be screened for appropriateness of inclusion for this study. The screen will include: questions regarding history of concussion, questions related to type of vestibular symptoms (dizziness, room spinning, imbalance, etc.), an oculomotor screen for gaze and spontaneous nystagmus, a Head Impulse Test, and a Dynamic Visual Acuity Test. Subjects will be excluded if they have a gaze nystagmus in room light, a convergence disorder detected with oculomotor screening, or are currently enrolled in vision therapy, as an adjunct treatment. These findings would indicate that the patient's diagnosis falls in a category not included in this study, or that visual disturbances would be a confounding factor during this study. If, following screening, the potential subject is determined to be appropriate for this study, informed consent will be obtained after the potential subject has all their questions answered to their satisfaction.

After informed consent has been obtained from a recruited subject, those with Unilateral Vestibular Hypofunction (UVH) will be asked to perform a 4-week intervention, while those with Bilateral Vestibular Hypofunction (BVH) or those post-concussion will each be asked to perform a 12-week intervention. Those with UVH will undergo a shorter intervention due to strong evidence that neural adaptation occurs much more quickly (usually 4 weeks) than those with BVH and history of concussion. The intervention will consist of physical therapy visits combined with a home program of specific vestibular exercises. Each subject will be asked to attend physical therapy visits at least one time per week throughout the 4- or 12-week period.

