Assessments will be performed on all groups and consist of a combination of vestibulo-ocular assessment, balance and clinical functional outcome measures, a survey regarding the usability of the virtual reality device, and surveys of subject satisfaction (see table below). Balance and functional outcome measures will include the Dizziness Handicap Inventory (DHI), Visual Analog Score (VAS) of symptoms, Visual Vertigo Analogue Scale, Functional Gait Assessment (FGA), Activities-Specific Balance Confidence (ABC) Scale, and the modified Clinical Test of Sensory Organization and Balance (CTSIB). Vestibulo-ocular assessment will be conducted using Frenzel goggles and will include tests of: Spontaneous Nystagmus, Gaze-evoked Nystagmus, Smooth Pursuit, Doll's Eyes, Head Impulse, Dynamic Visual Acuity, and Dix-Hallpike. Subjects will also perform the X1 vestibulo-ocular reflex exercise using the virtual reality device for a maximum of 30 seconds in incrementing levels. The X1 involves focusing on a stationary letter while

moving the head back and forth or up and down at approximately 1 cycle per second. If at any point the patient experiences an increase of 3 points on a scale of 0 (no dizziness) to 10 (worst imaginable) of symptoms, exercise in the device will stop. For instance, if a subject begins with a rating of 1/10 dizziness, they are instructed to stop if their symptoms reach a 4/10 or greater. Additionally, at weeks 4, 8 and 12, surveys would ask about patient comfort and level of satisfaction with regards to the intervention protocol. At the conclusion of their participation, subjects will be asked to complete the System Usability Scale to determine the usability of the virtual reality device. On each day of testing, subjects are free to skip any tests or questions they do not want to perform.

Subjects are randomly assigned to the usual rehabilitation or intervention group based on each of the following diagnostic categories: Unilateral Vestibular Hypofunction, Bilateral Vestibular Hypofunction, and post-Concussion. Therefore, there will be a total of three (3) usual rehabilitation and three (3) intervention groups (see table below). Additionally, there will be a seventh group consisting of healthy control subjects that have no history of vestibular symptoms.

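### The only dose regression states no diagnosis or baseline term, although diagnosis sets programme length; pooled across diagnoses, it could confound dose with diagnosis

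*Combined protocol and SAP*

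**What the plan says.** The title is "Dose of Vestibular Rehabilitation Required for Clinical Improvements in Individuals With Vestibular Hypofunction". The section headed Statistical Analysis Plan lists four analyses, and only the last concerns dose: "A multiple regression analysis will be used to determine the relationship between the exercise parameters and changes in outcome measures". No diagnosis term, baseline term, dose window or dose source is given there or elsewhere.

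Other parts of the document bear on that sentence:

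- **Programme length.** The Description gives UVH a 4-week programme, "while those with Bilateral Vestibular Hypofunction (BVH) or those post-concussion will each be asked to perform a 12-week intervention". The reason offered is that in UVH "neural adaptation occurs much more quickly (usually 4 weeks"). The group table follows suit: UVH is assessed at baseline and week 4, the other two diagnoses at baseline and weeks 4, 8 and 12.
- **Randomisation.** "Subjects are randomly assigned to the usual rehabilitation or intervention group based on each of the following diagnostic categories". The repeated-measures ANOVA in the Statistical Analysis Plan is likewise specified by diagnosis.
- **Dose recording.** In usual rehabilitation, "They will be asked to keep a log of their exercises to assess patient reported compliance". In the virtual reality (VR) arm the device records frequency and duration automatically.
- **Progression.** "Subjects should increase the duration and speed of the exercises as they are able". When background complexity rises, "the patient will be instructed to again start at 30 second exercise bout durations".

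**The concern.** Diagnosis is tied to both sides of this regression. At equal weekly minutes, a 12-week programme yields three times the total dose of a 4-week one (12/4 = 3). The protocol also expects recovery to run at a different speed in UVH. A variable linked to both exposure and outcome is a potential confounder. The regression sentence, read literally, has exercise parameters as its only predictors and does not carry over the split by diagnosis used for randomisation and for the repeated-measures ANOVA.

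Baseline severity raises a similar question. Change scores usually depend on the starting value, and progression here depends on symptoms, so severity may be related to dose as well as to change.

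At stake is the slope that would be reported as the answer to the title question. It could be too shallow, too steep or, in more extreme settings, of the wrong sign.

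**Working it through.** The documents give no sample size, dose, standard deviation (SD), slope or diagnosis mix, so there is no planned figure to reproduce. The only inputs taken from them are the 4-week and 12-week programmes. **Every other input below is assumed, and the results are illustrations.**

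**1. Total dose, pooled, no diagnosis term.** Assume 70 min/week in every diagnosis with SD s, a true slope of 0.02 points per minute (2.0 per 100 minutes), UVH share p, and a UVH advantage of A points that does not depend on dose. The gap in mean total dose is (12 - 4) x 70 = 560 minutes.

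- Within-diagnosis dose variance: W = p(4s)² + (1-p)(12s)²
- Between-diagnosis dose variance: B = p(1-p) x 560²
- Pooled slope = 0.02 - p(1-p) x 560 x A / (W + B)

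At p = 1/3 and s = 20, W = 40,533 and B = 69,689, which sum to 110,222. Slopes per 100 minutes:

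| A (points) | p = 1/3, s = 20 | Range over p = 20-50%, s = 10-30 |
|---|---|---|
| 0 | 2.00 | 2.00 |
| 5 | 1.44 | 1.19 to 1.71 |
| 11.2 | 0.74 | 0.19 to 1.36 |
| -5 | 2.56 | 2.29 to 2.81 |

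A = 11.2 (0.02 x 560) is the value at which all diagnoses have the same mean gain.

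The sign changes at A = 0.02(W + B) / [p(1-p) x 560]. This is 17.7 at p = 1/3 and s = 20, but runs from 12.3 (p = 50%, s = 10) to 35.0 (p = 20%, s = 30). The threshold is proportional to the assumed true slope, so it is not a property of this trial. In simulation at s = 20, adding a diagnosis term returned 2.00-2.01 throughout.

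**2. No true dose effect.** A separate simulation assumed 20 patients per diagnosis, 60 (SD 20) min/week, residual SD 15 points and two-sided 0.05. For UVH gaps of 0, 5, 10 and 15 points, the pooled model on total hours gave mean slopes of 0.00, -0.36, -0.70 and -1.08 points/hour and rejected in 5.0%, 14.4%, 41.4% and 73.6% of replicates. With diagnosis and arm terms it rejected in 4-5%.

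**3. Weekly dose.** If mean weekly minutes are equal across diagnoses, pooling does not bias the slope. If they differ by 10 min/week (p = 1/3, s = 20), the shift per 20 min/week is 20 x (2/9) x 10 x A / (400 + (2/9) x 100). That is 0.53 at A = 5 and 1.18 at A = 11.2, so a diagnosis term is still needed.

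**4. Weekly dose over windows that differ by diagnosis.** Under the truth in step 1, the slope per min/week is 0.02 x 4 = 0.08 in UVH and 0.02 x 12 = 0.24 in the others. A diagnosis main effect alone forces one slope. At p = 1/3 with equal weekly SD it is (1/3)(0.08) + (2/3)(0.24) = 0.19, which is right for neither group. Differing windows therefore need separate models or an interaction.

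**5. Two dose sources.** Assume equal arms, weekly dose SD 20, and a true slope of 5.0 per 20 min/week. Random error in the self-reported log, with reliability r, gives 5 x 400 / [400 + 0.5(400/r - 400)]: 3.3 at r = 0.5 and 4.4 at r = 0.8, with or without an arm term. Proportional over-reporting of 25-50% gives 3.8-2.6 (4.4-3.8 with an arm term). Over-reporting concentrated in low-dose subjects gave 4.3-5.5 in simulation (5.3-6.0 with an arm term).

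**6. What no added term removes.** If dose correlates -0.5 to +0.5 with dose-independent recovery of SD 10 points, a true slope of 0 appears as 0.5 x 10 = 5.0 points per SD of dose, in either direction.

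**The case against.** The strongest reply is that the harm belongs to a model that the plan never states. Randomisation and the repeated-measures ANOVA are both by diagnosis, so a by-diagnosis regression is a natural reading, and under it the confounding in steps 1 to 3 disappears. The protocol also undertakes to report additional physical therapy sessions as possible confounding information. And every magnitude above is invented.

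Most of this stands, and it limits the point. A reader might infer that the plan will give a biased dose estimate, that a real benefit will be masked or reversed, or that the model will be chosen after the data are seen. The documents support none of these. They state neither pooling nor cumulative dose. They say that UVH adapts faster, but not how much of the gain is independent of dose. They do not show when the model will be fixed.

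What does not stand is the suggestion that nothing needs changing. The by-diagnosis reading has to be borrowed from a neighbouring sentence, and reporting extra sessions addresses neither diagnosis nor baseline.

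On baseline, it is fair to say that a change score already subtracts the starting value and that no harm has been quantified here. The case rests on the general dependence of change on starting value and on symptom-led progression, not on a calculation.

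The sentence also leaves the parameters, the outcomes and the use of the self-reported log unnamed. That is missing detail, and it is not counted as an error of analysis.

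**Conclusion.** The point holds as a weakness in the stated model. The only analysis of the title question names exercise parameters and no diagnosis or baseline term, in a design where diagnosis sets a threefold difference in programme length and an expected difference in speed of adaptation. Fitted literally and pooled, it can confound dose with diagnosis.

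The bias is a risk left open by the text. It vanishes if the regression is fitted by diagnosis, if diagnoses do not differ apart from dose, or if dose is weekly with equal means across diagnoses. Its size and sign cannot be derived from the documents. The illustrations show only that moderate assumed differences move the slope materially in either direction, and that the point of sign reversal shifts widely with the assumptions. The plan should be corrected, but nothing here shows that its result will be wrong.

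**What to change.** Amend the Statistical Analysis Plan as follows.

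- **Model.** Fit the dose regression separately within each diagnosis, as the repeated-measures ANOVA already is, and adjust for the baseline value of the outcome.
- **If diagnoses are combined.** Use weekly dose and outcome change over the common window, weeks 0-4, with a diagnosis term. This still assumes one slope for all diagnoses, which a dose-by-diagnosis interaction can examine if numbers allow.
- **If windows differ** (weeks 0-4 for UVH, 0-12 for the others). Use separate models or a dose-by-diagnosis interaction. A diagnosis main effect alone is not enough.
- **Dose source.** Use device-logged dose from the VR arm for the main estimate or as a sensitivity analysis. If self-reported dose is also used, first confirm that the log records usable dose, then include arm and state that an arm term does not remove reporting error within the arm.
- **Interpretation.** Report the slope as an association. Dose is not randomised and progression depends on symptoms. Even its direction of effect on minutes is not fixed, because bouts shorten again when complexity rises.

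The cost is wording: diagnosis is the randomisation stratum and baseline scores are already collected. Self-reported dose is the exception, since the protocol does not say that the log records minutes or sessions. In a combined model the terms use 2 degrees of freedom for diagnosis, 1 for baseline, 1 for arm and 2 for each interaction. With no sample size given, whether an interaction is affordable cannot be judged. By-diagnosis estimates are less precise, and a device-only estimate has a standard error about 1.4 times (√2) as large if arms are equal.
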